8.3.3. Covariates

Patient demographics, clinical characteristics, comorbidities, and concomitant medications will be measured during baseline period and index date, and identified by Read Medical Codes,

Comparative Effectiveness and Safety of DOACs in Patients with AFib in the UK

ICD-10 diagnosis codes, and medication ATC codes for corresponding covariates. These covariates include cohort entry year, age, sex, socioeconomic indicators (e.g., marital status), and selected components of CHA₂DS₂ VASc stroke risk score^{27,28} (heart failure, hypertension, and diabetes), and ORBIT-AF bleeding risk score in AFib patients^{29,30} (heart failure, renal impairment, hepatic impairment; osteoporosis/hip fractures, anemia, antiplatelet therapy, aspirin therapy, NSAIDs therapy, and smoking and alcohol drinking history [if available]).

Additional comorbidities and concomitant medications deemed to be associated with the primary and secondary outcomes of interest will be included in the analyses. All covariates will be determined based on the literature and clinical knowledge. The operational definitions of each covariate will be recorded in the STaRT-RWE template and are available on request.

9. Data Analysis

Data analyses will be performed in a stepwise approach involving three distinct sequential phases (Figure 9.1): *Exploratory Phase* (data explorations will be done in advance to inform key design decisions), *Diagnostic Phase* (requirements that must be met prior to viewing study outcomes, e.g. covariate balance), and *Inferential Phase* (comparative analyses).

[figure not shown]

Figure 9.1 Data Analysis Phases

In the *Exploratory Phase*, the study implementation team completed explorations related to the patient selection criteria, exposure groups, and outcome definitions that informed the development of the study protocol.

For the *Diagnostic Phase*, the checklist in Table 9.1 must be satisfactorily completed prior to beginning the implementation of the *Inferential Phase*. As such, the relationship between the exposure and outcome of interest will not be described or evaluated in the analytic dataset until the study implementation team reaches consensus that the diagnostic criteria are satisfied.

Table 9.1 Diagnostic Checklist to Complete Prior to Progression to the Inferential Phase

Diagnostic Criteria	Description

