Confirm adequate sample size	
Adequate sample size will be defined as the minimum sample size required to achieve 80% power to detect a HR of ≥ 0.80 for the primary outcome of stroke under the assumptions of 1:1 matching ratio of the primary comparators (apixaban vs. rivaroxaban); a false-positive rate $\alpha=0.05$; a 1-sided test; and a background stroke incidence rate of 47 events per 100,000 person-years in patients with AFib³¹
 
Note: If adequate sample size is not reached (i.e., minimum HR

Comparative Effectiveness and Safety of DOACs in Patients with AFib in the UK

	
that we can detect is <0.80), it will not solely prohibit us from moving on to interventional analysis. NICE would typically use treatment effect estimates to parameterise economic models and as long as the uncertainty in estimates is quantified, it can be accounted for in decision-making. In addition, a recent article³² deprioritized the importance of power calculations for observational studies, noting that observational analyses with imprecise effect estimates should be completed as small studies can be pooled to provide a more precise effect estimate. Therefore, this analysis is informative even if the sample size is insufficient to detect a HR ≥ 0.80 with 80% power.

Confirm positivity of variables	
Propensity score distributions will be visually inspected, and overlap in all areas of the propensity score distributions will be confirmed.
 
Other approaches, such as propensity score weighting, will be explored to achieve covariate balance in case propensity score matching is insufficient.

Confirm baseline confounder balance	
The distributions of all potential confounders will be confirmed to be balanced for each comparison of interest. Covariate balance will be defined as ASD ≤ 0.10.
 
Although covariates with balance prior to propensity score matching may be removed from the propensity score model, balance of these covariates will still be confirmed after matching. Covariates with small residual imbalance (defined as $0.10 \leq \text{ASD} \leq 0.15$) may be deemed balanced if the covariate does not predict the outcome among the referent group (defined as ASD < 0.10 when comparing the risk of the outcome in those with the covariate vs. those without it) Evaluation of imbalance in outcome prediction will only be conducted once at the end of the diagnostic phase if all other diagnostic criteria are met.

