Confirm models are not overfit	All models must contain ≥ 12 exposed patients per covariate
Confirm persistence of treatment	
Initiators of DOACs stay on treatment for a substantial amount of time after starting treatment. The definition of "substantial persistence" will be finalized during the diagnostic phase and will be data driven.
 
If substantial crossover or censoring is observed, appropriate methods to account for these censoring issues will be applied in the comparative analyses.
 
Preliminary analyses show patients treated with DOACs in the database have a median follow-up of 2.3 years (IQR, 1.0-3.9). In clinical trials, the median duration of treatment was 1.5 years.

Unless otherwise specified, results will be provided as descriptive statistics with categorical variables reported using frequency distributions, and continuous variables reported using means, standard deviations, medians, minimums, maximums, 25th percentiles and 75th

Comparative Effectiveness and Safety of DOACs in Patients with AFib in the UK

percentiles. For inferential statistics, both crude and covariate adjusted analyses will be reported for study outcomes.

Among patients in each of the exposure groups, the incidence rates and 95% confidence intervals (CI) of stroke and secondary outcomes will be calculated for each of the mutually exclusive comparison groups, along with the number of events, total number of individuals, and accrued person-time. Incidence rates will be calculated as the number of incident outcomes of interest within the follow-up period divided by the total person-time at-risk, and reported as rate per 1,000 person-years.

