In each comparison cohort, multivariable logistic regression will be used to estimate the probability of a patient's initiation of the exposure given baseline covariates and cohort entry year (i.e., the propensity score). Propensity score matching between exposure groups will be performed using 1:1 nearest neighbor matching without replacement with a maximum matching caliper of 0.01. In addition to graphical depictions of propensity score distributions, the absolute standardized differences (ASD) in proportions and means of baseline characteristics will be estimated to examine comparability of exposure groups. Covariates with $ASD \leq 0.10$ are considered balanced between comparator groups.³³ Covariates with small imbalances $0.10 \leq ASD \leq 0.15$ may be deemed balanced if the covariate does not predict the outcome among the referent group.

Cox proportional hazards regression (outcomes model) will be used to estimate hazard ratios (HR) and 95% CI for each outcome after propensity score matching. The incidence of stroke and secondary outcomes will be compared between individual DOACs in primary and secondary comparisons as mutually exclusive cohorts.

Subgroup analyses that will be considered include DOACs initiators with prior warfarin use; age (<75 and ≥ 75 years); concomitant aspirin use; CHA₂DS₂ VASc score (0-1, 2-3, and ≥ 4), and selected comorbid conditions, e.g. diabetes, heart failure, and BMI status (<30 and ≥ 30 kg/m²).

Sensitivity analyses will be performed to assess the impact of varying the study period on study findings by limiting analyses on data up to February 28, 2020 to account for potential impact of COVID-19 pandemic on healthcare utilization.

Additionally, high-dimensional propensity score (HdPS) analysis will be used as a sensitivity analysis to estimate the association between treatment with DOACs and the primary outcome of stroke. The HdPS approach is a 7-step algorithm that empirically identifies a pool of covariates from different data dimensions based on their prevalence, and then selects a subset of the covariates for inclusion in a propensity score model based on their potential to bias the exposure-outcome association.³⁰

Missing values will be reported as missing, and no imputation will be undertaken. All data analysis will be conducted using Aetion Evidence Platform® (2021), software for real-world data analysis. Aetion, Inc. <https://www.aetion.com>.

10. Limitations of the Research Methods

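### Table 9.1 lets covariates that look balanced before matching leave the propensity score model; a dropped outcome predictor can then pass the re-check with an imbalance near 0.10 SD that keeping it would nearly remove

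*Protocol*

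**What the plan says.** Section 8.3.3 selects covariates on subject-matter grounds: "All covariates will be determined based on the literature and clinical knowledge". It includes further comorbidities and medications because they are thought to be related to the outcomes.

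Section 9 fits a propensity score in each comparison cohort and applies "1:1 nearest neighbor matching without replacement with a maximum matching caliper of 0.01". Covariates with an ASD of at most 0.10 "are considered balanced between comparator groups".

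In Table 9.1, the row on confounder balance does four things:

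- It sets the threshold: "Covariate balance will be defined as ASD ≤ 0.10".
- It gives the permission: "Although covariates with balance prior to propensity score matching may be removed from the propensity score model".
- It attaches the safeguard: "balance of these covariates will still be confirmed after matching".
- It tolerates an ASD of 0.10 to 0.15, in that such a covariate "may be deemed balanced if the covariate does not predict the outcome among the referent group".

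The row on overfitting limits model size: "All models must contain ≥ 12 exposed patients per covariate".

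Section 10 undertakes to try to include all potential confounders in the propensity score analysis. It also points to the high-dimensional propensity score sensitivity analysis, which section 9 specifies for stroke.

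**The concern.** Covariates enter the list because they are believed to predict outcome, but they may leave the model on a screen that ignores outcome prediction and looks only at the crude difference between groups. That screen is marginal. Matching on the remaining covariates changes the composition of both groups, so the difference in a dropped covariate can persist, shrink or grow.

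The re-check catches only what ends above 0.10. Below that, an imbalance in an outcome predictor is accepted although the model could have removed it. The resulting bias is not reflected in the confidence interval. That matters here because Table 9.1 says the estimates would typically feed economic models as long as their uncertainty is quantified.

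There is also a tension within the document. Section 10 aims to include all potential confounders, while Table 9.1 allows some to be left out for a reason unrelated to their importance.

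**Working it through.** The protocol states no bias figure, cohort size or covariate strength for this point, so there is no figure to reproduce. Two questions can be checked under stated assumptions.

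**1. How far can one covariate at the ceiling move the hazard ratio?**

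From the protocol: ASD ceiling 0.10; target hazard ratio 0.80 (Table 9.1), used only as a scale. Assumed: covariate strength and prevalence.

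- Continuous covariate: factor = exp(ASD × ln HR per SD). At ASD 0.10 and HR per SD of 1.2, 1.5 and 2.0 this gives 1.018, 1.041 and 1.072.
- Binary covariate: factor = [1 + p1(HR − 1)] / [1 + p0(HR − 1)], with p1 solved from the ASD. At p0 = 0.10, an ASD of 0.10 gives p1 = 0.132; with HR 1.5 the factor is 1.066 / 1.050 = 1.015. At p0 = 0.30, p1 = 0.3467; with HR 2.5 it is 1.520 / 1.450 = 1.048. Over prevalences of 10% to 50% and HR 1.5 to 2.5 the range is 1.015 to 1.048.

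One covariate at the ceiling therefore shifts the hazard ratio by about 1.5% to 7%. If the bias is upward, a true 0.80 would be estimated as 0.80 × 1.015 = 0.81 up to 0.80 × 1.072 = 0.86.

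For several covariates the exponents add, if the covariates are independent, all at the ceiling and all in one direction. For HR per SD of 1.2 to 1.5, three give 1.06 to 1.13 and five give 1.10 to 1.22. These are upper bounds.

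**2. Does dropping leave an imbalance that keeping would remove?**

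Simulation with assumed structures: n = 10,000, 15 replicates per setting, five retained covariates (log-odds of treatment 0.3 each) and five candidates for dropping. Logistic propensity score, 1:1 nearest-neighbor matching without replacement, caliper 0.01. The three ASD columns are means over the five candidates.

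| Candidates' relation to retained covariates and treatment | Before matching | After, if dropped | After, if kept | Matched pairs, dropped → kept |
|---|---|---|---|---|
| Independent, own link to treatment | 0.081 | 0.089 | 0.001 | 3,753 → 3,684 (−1.8%) |
| Correlation 0.3, opposing link | 0.003 | −0.079 | 0.000 | 3,848 → 3,782 (−1.7%) |
| Correlation 0.5, opposing link | 0.049 | −0.068 | 0.002 | 3,946 → 3,881 (−1.7%) |
| Correlation 0.5, stronger opposing link | 0.001 | −0.111 | 0.002 | 4,031 → 3,874 (−3.9%) |
| Correlation 0.3, no link of their own | 0.082 | 0.001 | 0.002 | 3,728 → 3,722 (−0.2%) |

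When the candidates were kept, the largest absolute ASD among the five averaged 0.013 to 0.017. When they were dropped, it averaged 0.119, 0.105, 0.088, 0.130 and 0.038 in row order. In the first two rows the re-check would thus often flag at least one candidate while passing others. In the third row all five would typically pass. In the fourth the average candidate is flagged. In the fifth there is nothing to flag.

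**The case against.** The case for leaving the text alone is substantial, and several parts of it stand.

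- **The safeguard is real.** Removal is optional, the re-check is in the same sentence, and the checklist must be completed before exposure and outcome are related. The fourth row of the simulation would be caught, and the fifth shows that dropping can be harmless. So the permission *can* leave an imbalance; it does not necessarily do so.
- **The 0.10 threshold is the protocol's declared standard** and applies equally to retained covariates. That stands. But retained covariates usually end far below it, whereas a dropped one may sit close to it for no gain.
- **A reader might infer that a dropped outcome predictor may drift to 0.15.** The text does not support this: the wider band is open only to covariates shown not to predict the outcome in the referent group.
- **A reader might infer that keeping everything is free because the cohorts are large.** The protocol gives no cohort size, plans for an inadequate one, and names edoxaban and dabigatran as comparison groups while describing apixaban and rivaroxaban as the most prescribed. The limit of 12 exposed patients per covariate could bind in the smaller groups, and some matched pairs are lost.
- **A reader might infer that the bias could swallow the target effect.** That needs about five independent covariates, all at the ceiling and all pointing the same way (0.80 × 1.22 = 0.98 at HR 1.5 per SD). Nothing in the document suggests this pattern. Many of the listed covariates are binary, with an SD of at most 0.5, so an HR of 2.0 per SD would mean a covariate HR of at least 4.
- **The high-dimensional propensity score analysis offers some protection**, but it is a sensitivity analysis and is specified for stroke only.

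**Conclusion.** The point holds as a cheap improvement of minor to moderate weight. The permission allows an outcome predictor to leave the model on crude balance alone, and the re-check can accept an imbalance near 0.10 SD. In the simulated settings where the dropped covariates had their own link to treatment, the mean absolute ASD after matching was about 0.07 to 0.11, against about 0.00 when they were kept.

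The likely effect of one such covariate at the ceiling is a shift of 1.5% to 7% in the hazard ratio, or roughly 7% to 31% of the target effect on the log scale (0.015 / 0.223 to 0.069 / 0.223, where 0.223 = |ln 0.80|). The ASD of 0.10 is an imbalance in the covariate, not itself the bias in the hazard ratio. These sizes rest on assumed covariate strengths, prevalences and correlations, none of which the protocol gives.

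No stated figure is wrong. The conflict with section 10 is one of intent, since that section speaks of efforts and Table 9.1 of an option, but the two should be made consistent.

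**What to change.** Replace the permission in Table 9.1 with:

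> All prespecified covariates enter the propensity score model whatever their balance before matching; a covariate is dropped only for non-estimability or to meet the criterion of at least 12 exposed patients per covariate.

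Keep the balance check after matching for every covariate, including any dropped under these exceptions. This brings Table 9.1 into line with sections 8.3.3 and 10.

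The cost is one sentence and slightly fewer matched pairs (about 0.2% to 3.9% in the simulation at n = 10,000, under its assumed structures). In the smaller comparison groups the model-size rule may still force some covariates out, and the wording allows for that.

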8.3.2. Outcomes

The primary outcome is ischemic or hemorrhagic stroke. Secondary outcomes include the occurrence of all-cause mortality, myocardial infarction, transient ischemic attacks, major bleeding events, and major adverse cardiovascular events (MACE). Major bleeding is defined as a composite outcome of major intracranial (including hemorrhagic stroke), gastrointestinal, and urogenital bleeds. MACE outcomes will be a composite endpoint of angina, myocardial infarction, and stroke.

Outcomes of interest will be measured during the study follow-up period, and defined by corresponding Read Medical Codes and ICD-10 diagnosis codes at the primary care setting. The operational definitions of each outcome will be recorded in the STaRT-RWE template and are available on request.

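### The balance waiver tests whether a covariate predicts the outcome with a standardized risk difference, which misses moderate to strong predictors when the outcome is as rare as stroke

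*Protocol*

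**What the plan says.** Protocol section 9, Table 9.1 (row on baseline confounder balance), sets ASD 0.10 or less as the standard after matching. It then makes an exception: a covariate with ASD between 0.10 and 0.15 "may be deemed balanced if the covariate does not predict the outcome among the referent group". The table gives non-prediction a number, namely an outcome ASD under 0.10 "when comparing the risk of the outcome in those with the covariate vs. those without it". The propensity-score paragraph later in section 9 repeats the exception without the number.

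The check is run once, at the end of the diagnostic phase, and only if the other criteria are met. The 0.10 cut-off is the same for every outcome and is not adapted to how common the outcome is. For the main analysis, "The primary outcome is ischemic or hemorrhagic stroke".

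**The concern.** The exception is sound in principle: a covariate unrelated to the outcome cannot confound. The difficulty is the yardstick. For a binary outcome the ASD divides the risk difference by roughly the square root of p(1−p). When p is small, a large relative risk is still a small risk difference, and the ASD stays low. Bias in a hazard ratio follows the relative risk. A cut-off borrowed from covariate balance therefore does not measure prognostic strength for a rare event.

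A real stroke predictor could be labelled non-predictive and left imbalanced. Section 9 specifies a Cox model after matching and does not say that a waived covariate enters it. Section 8.3.3 lists heart failure, hypertension and diabetes as covariates because they are components of a stroke risk score, so covariates of this kind are the ones the test has to recognise.

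**Working it through.** The plan states no figure that can be reproduced here: it gives no number of patients or events and no derivation of the 0.10 limit for outcome prediction. The check is how strong a predictor must be before the rule notices it.

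**Inputs from Table 9.1**
- Waiver band: covariate ASD 0.10 to 0.15. Outcome limit: ASD 0.10.
- Planning rate: "a background stroke incidence rate of 47 events per 100,000 person-years in patients with AFib".
- Follow-up: median 2.3 years (IQR 1.0 to 3.9).
- Effect of interest: "80% power to detect a HR of ≥ 0.80 for the primary outcome of stroke".

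**Assumptions**
- The covariate is binary, and risk is cumulative over follow-up (the protocol does not state the horizon).
- Alternative non-carrier risks are 1%, 2% and 3%.
- Covariate prevalence is 30% in one exposure group.

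**Step 1: outcome ASD.** With p0 the risk without the covariate and p1 the risk with it,

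ASD = |p1 − p0| / √{[p1(1−p1) + p0(1−p0)]/2}.

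**Step 2: planning rate.** p0 = 1 − exp(−0.00047 × 2.3) = 0.00108. A covariate that doubles the risk has p1 = 0.00216 and ASD ≈ 0.00108/0.0402 = 0.027, about a quarter of the limit. A risk ratio (RR) of 3 gives 0.047.

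**Step 3: largest RR that passes.** Solving ASD = 0.10 for p1:

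| Non-carrier risk p0 | p1 at the limit | Largest passing RR |
|---|---|---|
| 0.108% (planning rate, 2.3 years) | 0.767% | 7.1 |
| 1% (assumed) | 2.27% | 2.3 |
| 2% (assumed) | 3.66% | 1.8 |
| 3% (assumed) | 4.95% | 1.65 |

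At the planning rate the limit is RR 13.3 over 1.0 year and about 5.1 over 3.9 years.

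**Step 4: when a doubling is caught.** Setting p1 = 2p0 and ASD = 0.10 gives p0² = 0.01(3p0 − 5p0²)/2, so p0 = 0.015/1.025 = 1.46%. Over 2.3 years this is −ln(1 − 0.0146)/2.3, or about 6.4 per 1,000 person-years. Below that a doubling passes; above it, it is caught.

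**Step 5: bias from one waived covariate.** With prevalences q0 and q1 in the two exposure groups, bias factor = [1 + q1(RR − 1)] / [1 + q0(RR − 1)]. With q0 = 0.30, a covariate ASD of 0.10 means q1 = 0.347 and an ASD of 0.15 means q1 = 0.371.

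| RR | At ASD 0.10 (ordinary limit) | At ASD 0.15 (top of waiver band) | Added by the waiver |
|---|---|---|---|
| 1.8 | 1.277/1.240 = 1.030 | 1.296/1.240 = 1.046 | about 1.5 points |
| 2.2 | 1.416/1.360 = 1.041 | 1.445/1.360 = 1.062 | about 2 points |

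**Step 6: scale.** The target effect is |ln 0.80| = 0.223. At ASD 0.15 the bias is ln 1.046/0.223 ≈ 20% of it for RR 1.8 and ln 1.062/0.223 ≈ 27% for RR 2.2. At ASD 0.10 the shares are about 13% and 18%. Two independent covariates of RR 1.8, imbalanced in the same direction at ASD 0.15, give 1.046² ≈ 1.09, against 1.030² ≈ 1.06 at the ordinary limit.

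**The case against.** The strongest reply concerns scale, and much of it stands.

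- **Most of the bias is not due to the waiver.** A reader might attribute the whole 4.6% to 6.2% to it. The ordinary 0.10 standard already tolerates 3.0% to 4.1%.
- **The RR of 7 depends on the rate.** The check would use the observed referent-group risk, not a sample-size assumption. The reference list gives that rate's source as a population stroke study, whereas this cohort has atrial fibrillation plus a further stroke risk factor. A reader might infer that any covariate doubling the risk slips through; that holds only below about 1.46% non-carrier risk.
- **The waiver is not automatic.** If 0.108% is read as the overall risk and 30% carry the covariate, the outcome ASD cannot exceed about √(2 × 0.0036) = 0.085, since 0.00108/0.30 = 0.0036 even if every stroke occurs in carriers. A reader might conclude that the waiver always applies. That is a different basis from the RR of 7, which takes 0.108% as non-carrier risk. Moreover, the text is permissive (*may*), progression needs team consensus, and covariates above 0.15 still fail. Nothing shows that any covariate will land in the band.
- **The outcome look is limited.** It is confined to the referent group and done once, so it does not expose the treatment comparison.
- **Damage to every secondary hazard ratio is not shown.** The weakness shrinks as outcomes become commoner.

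The protocol's other safeguards do not cure the defect. Weighting is to be explored when matching is insufficient, but a covariate deemed balanced need not trigger it. The high-dimensional propensity score is a sensitivity analysis for stroke only. Section 9 promises covariate-adjusted results in general terms but does not commit to adjusting for a waived covariate. The word *may* leaves discretion, yet the only criterion offered for using it is the insensitive one.

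**Conclusion.** The point holds as a should-fix. Table 9.1 fixes a numeric test of non-prediction that is insensitive for rare outcomes: it passes risk ratios up to about 7 at the planning rate, and up to about 2.3, 1.8 and 1.65 at assumed non-carrier risks of 1%, 2% and 3%. The extra bias attributable to the waiver is modest, at most about 1.5 to 2 percentage points per covariate in the example, and it arises only if a covariate falls in the 0.10 to 0.15 band and the team uses the exception. Several waived covariates pulling the same way would add up. The problem is greatest for stroke and other rare outcomes.

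These figures assume a binary covariate, 30% prevalence and cumulative risk over the stated follow-up. They do not establish that the primary result will be materially biased.

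**What to change.** In Table 9.1 and the matching paragraph of section 9, stop using an outcome ASD below 0.10 as the test of non-prediction. For any covariate with ASD above 0.10 after matching, re-specify the propensity score. If the imbalance persists, include that covariate in the Cox outcome model for that comparison.

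An acceptable alternative keeps the exception but judges prediction on a relative scale: a hazard or risk ratio, or a pre-set limit on the bias factor implied by the residual imbalance and the covariate's association with the outcome.

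The cost is a couple of sentences in the protocol and a few extra model terms where imbalance remains. The first option also removes the need to look at outcomes during the diagnostic phase.
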